[name] Clinical Project Leader	Laboratoires THÉA Department of Research and Development [name] [name] [contact] [contact] Email: [contact]

CIP Synopsis

Title	Comparison of the performance and safety of T2259 versus Vismed® Multi in dry eye patients with superficial keratitis.
Sponsor	Laboratoires Théa
Sponsor Investigation No.	LT2259-001
International Coordinating Investigator	[name]
Investigation Centre(s)	This investigation is planned to be carried out at approximately 35 sites in France, in Spain, in Slovakia and in Poland.
Planned Schedule	
 ▪ Planned initiation: October 2018 ▪ Planned last patient last visit: December 2020
Primary Investigation Objective	The primary objective of this study is to demonstrate the non-inferiority of T2259 versus Vismed® Multi in terms of performance.
Secondary Investigation Objective(s)	To evaluate the safety and performance of T2259 versus Vismed® Multi.
Primary Performance criterion	
 ▪ Change from baseline in total ocular staining grade according to Oxford 0-15 grading scheme (corneal staining by fluorescein, nasal and temporal conjunctival staining by lissamine green) at Day 35 in the worst eye.
Secondary Performance criteria	
 • Change from baseline in total ocular staining grade according to Oxford grading scheme at Day 8 and Day 84 in the worst eye and at Day 8, Day 35 and Day 84 for contralateral eye. • Change from baseline in Van Bijsterveld score* (lissamine green staining) at Day 8, Day 35 and Day 84. • Change from Day1-10/Day1-7 (selection visit) in DEQ-5 at Day 35 and Day 84. • Change from baseline in OSDI (Ocular Surface Disease Index) score at Day 8, Day 35 and Day 84. • Change from baseline in Schirmer test result* (without anaesthesia) at Day 8, Day 35 and Day 84. • Change from baseline in TBUT* (Tear Break-Up Time) at Day 8, Day 35 and Day 84. • Conjunctival hyperaemia* using McMonnies photographic scale at Day 8, Day 35 and Day 84. • HLA-DR (AUF) at Day 84 in Right Eye if eligible eye. • Objective Scatter Index (OSI) at Day 35 and Day 84. • Dry Eye symptoms: burning/irritation, stinging/eye pain, itching, eye dryness feeling, foreign body sensation, light sensitivity and fluctuating blurred vision evaluated with a 4-level verbal scale (0 = Absent; 1 = Mild, Present but not disturbing; 2 = Moderate, Disturbing, but not limiting daily activities; 3 = Severe, Very distressing and interfering with daily activities) and change from baseline in total score of Dry Eye symptoms at Day 8, Day 35 and Day 84.

	
 Performance assessment by the investigator (Unsatisfactory, Not very satisfactory, Satisfactory, Very satisfactory) at Day 35 and Day 84. 
*Assessment recorded for each eye will be analysed for the worst eye and the contralateral eye.

Safety parameters	
 Ocular symptoms upon instillation at Day 8, Day 35 and Day 84: burning/irritation, stinging/eye pain, itching, eye dryness feeling, foreign body sensation, light sensitivity and other symptoms evaluated with a 4-level verbal scale (0=Absent, 1=Present but not disturbing, 2=Disturbing but not limiting daily activities, 3=Very distressing and interfering with daily activities). Far best-corrected visual acuity (in logMAR) at Day 84. Tolerance assessment by the patient and the investigator using a 4-point verbal scale (Unsatisfactory, Not very satisfactory, Satisfactory, Very satisfactory) at Day 35 and Day 84. Ocular and systemic adverse events (AE/SAE).
Statistical method	
The aim of the study is to demonstrate the non - inferiority of T2259 with regard to Vismed® Multi in terms of performance.
 
The primary performance criterion is the change from baseline of total ocular staining grade in the worst eye on Day 35, evaluated using Oxford 0-15 grading scheme.
 
As the statistical hypothesis is the non-inferiority of T2259 with regard to Vismed® Multi, the main analysis of the primary criterion will be performed in the Per protocol population.
 
A total of 76 patients (i.e. 38 per treatment group) assume at least 90% power to establish the non-inferiority comparison on a one-sided two sample t-test with alpha=2.5 % basis (equivalent to a 95% two-sided confidence interval), assuming that the standard deviation is 2.5 and no difference between the 2 groups with a non-inferiority limit set at 2 for the change in total ocular staining grade.
 
Estimation of the standard deviation and determination of the non-inferiority limit are based upon data of previous studies and literature.
 
Concerning the non - inferiority limit, according to clinicians, a variation of 2 points in the total Oxford grade, which corresponds to a variation of less than 1 grade in the three areas (corneal, temporal and nasal), is considered as not clinically significant.
 
For taking into account approximately 15% of patients non-evaluable in Per protocol analysis (premature withdrawals without performance evaluation, patients with major protocol deviation), a total of 90 patients should be randomised in the study.

Sample size	90 randomised patients.										
Investigation Design	Multicentre, randomised study, investigator-masked, 2 parallel groups (T2259 versus Vismed® Multi) of 38 evaluable patients each.										
Investigation Duration	Run-in-period with preservative free artificial tears (Hydrabak®): from Day 1-10 or Day 1-7 to randomisation visit (Day 1) (one drop in each eye 3 to 6 times daily). 
 ▪ Treatment period: 84 ± 7 days ▪ Total study duration: maximum of 101 days 										
Investigational Medical Device(s) (IMD)	
T2259
 
Formulation: Trehalose, 6% ; Sodium Hyaluronate, 0.2%
 
Route of administration: Eye drops
 
Daily dose regimen: One drop in each eye 2 to 4 times daily.
 
Vismed® Multi
 
Formulation: Sodium Hyaluronate, 0.18%
 
Route of administration: Eye drops
 
Daily dose regimen: One drop in each eye 2 to 4 times daily.
										
Investigation Visits	
 
 Day 1-10/Day 1-7	Selection visit (Visit 1)	
 
 Day 1	Randomisation visit (Visit 2)	
 
 Day 8 (± 1)	Visit 3 Optional Visit (if the investigator and/or the patient thinks it is necessary.)	
 
 Day 35 (± 3)	Visit 4	
 
 Day 84 (± 7)	Final visit (Visit 5)	
 
 
Visits V2, V3, V4 and V5 should be performed at the same hour (± 4 hours)
	Day 1-10/Day 1-7	Selection visit (Visit 1)	Day 1	Randomisation visit (Visit 2)	Day 8 (± 1)	Visit 3 Optional Visit (if the investigator and/or the patient thinks it is necessary.)	Day 35 (± 3)	Visit 4	Day 84 (± 7)	Final visit (Visit 5)
Day 1-10/Day 1-7	Selection visit (Visit 1)										
Day 1	Randomisation visit (Visit 2)										
Day 8 (± 1)	Visit 3 Optional Visit (if the investigator and/or the patient thinks it is necessary.)										
Day 35 (± 3)	Visit 4										
Day 84 (± 7)	Final visit (Visit 5)										
Inclusion Criteria at selection visit	
1.1. Informed consent signed and dated.
 
1.2. Male or female aged ≥ 18 years old.
 
1.3. Known Dry Eye Syndrome requiring artificial tears within the last 3 months prior to study selection.
										
Inclusion Criteria at Randomisation visit (Day 1)	
1.4. Patient having used only unpreserved artificial tears (Hydrabak®) as ocular medication during the run-in period (from Day 1-10/Day 1-7 to Day 1).
 
1.5. No ocular instillation at least 6 hours prior to the randomisation visit (Day 1).
 
1.6. Diagnosis of moderate to severe dry eye syndrome defined by OSDI Score ≥ 23.
 
1.7. Patients having at least one Eligible Eye, defined by both following conditions:
 
 - Total ocular staining (corneal and conjunctival) with Oxford 0-15 grading scheme ≥ 4 and ≤ 9. 
AND
 
 - At least one of the following objective signs: 
Schirmer test ≥ 3 mm/5 min and ≤ 9 mm/5 min
										

	
Or
 
TBUT : sum of 3 measurements \leq 30 seconds.

Exclusion Criteria At selection visit	
Ophthalmic Exclusion Criteria in AT LEAST ONE EYE
 
2.1.1. Far best-corrected visual acuity \leq 2/10.
 
2.1.2. Severe blepharitis (grade 3 / 0-3 scale).
 
2.1.3. Ocular rosacea.
 
2.1.4. Severe Dry Eye associated to:
 
 - Eyelid malposition, - Corneal dystrophy, - Ocular neoplasia, - Filamentous keratitis, - Corneal neovascularisation, - Orbital radiotherapy. 
2.1.5. History of ocular trauma, ocular infection or ocular inflammation within the last 3 months.
 
2.1.6. History of ocular allergy.
 
2.1.7. History of uveitis.
 
2.1.8. History of inflammatory corneal ulcer within the last 12 months.
 
2.1.9. Glaucoma, ocular hypertension requiring glaucoma treatment.

Exclusion Criteria (continued)	
Systemic/non Ophthalmic Exclusion Criteria
 
2.2.1. Known or suspected hypersensitivity to one of the components of the Investigational Device or auxiliary products.
 
2.2.2. History of active relevant systemic condition incompatible with the study or likely to interfere with the study results or the patient safety according to investigator judgment.
 
2.2.3. Allergic rhinitis active or susceptible to reactivate during the study.
 
2.2.4. Any other medical or surgical history, disorder or disease susceptible to require or to modify systemic medication during the study (systemic medication having to be stable within the three months before selection).
 
Specific Exclusion Criteria Regarding Childbearing Potential Women
 
2.3.1 Pregnancy or breastfeeding.
 
2.3.2 Childbearing potential woman who is not using a reliable method of contraception (oral contraceptive, intra-uterine device, subcutaneous

	
contraceptive implant, vaginal ring, patch) and is not surgically sterilised.

Exclusion Criteria Related to General Conditions
	

2.4.1. Inability of patient to understand the study procedures or to give informed consent.
 
2.4.2. Non-compliant patient (e.g., not willing to attend a visit or completing the self-questionnaire; way of life interfering with compliance).
 
2.4.3. Participation in this investigation at the same time as another clinical investigation.
 
2.4.4. Participation in this investigation during the exclusion period of another clinical study.
 
2.4.5. Patient previously randomised in this study.
 
2.4.6. Patient being institutionalised because of legal or regulatory order, inmate of psychiatric wards, prison or state institutions, or employee of the study sites or of the sponsor's company.
 
2.4.7. Patient not covered by the government health care scheme of the country in which he/she is living.
 
2.4.8. Patient under guardianship/ward of court
	
Schedule of Assessments	For further details, refer to the schedule of assessments as flowchart study.

Table 1 Prohibited treatments (medications/non-medicinal therapies/procedures)

CONCOMITANT MEDICATIONS/NON-MEDICINAL TREATMENTS NOT ALLOWED BEFORE AND DURING THE INVESTIGATION						
Before the selection visit (Before Day 1-10/Day 1-7)					Run-in period (From Day 1-10/Day 1-7 to Day 1)	After randomisation (Day 1 to Day 84)
12 months	6 months	3 months	1 month	1 week	Run-in period	Treatment period
Corneal surgery,						
Intraocular injections.....						
	Other ocular surgeries (e.g. cataract, palpebral).....					
	Isotretinoïde, cyclosporine, tacrolimus, sirolimus, pimecrolimus.....					
	Any change in systemic medication already ongoing before selection visit.....					
	Permanent punctal plugs.....					
	Semi-permanent or temporary punctal plugs.....					
	Contact lenses.....					
					Any ocular medication other than Hydrabak®	
						Any ocular medication including artificial tears other than authorized medical devices

Table 2 Schedule of Visits and Procedures

STUDY PROCEDURE	Visit #1 Selection visit D1-10/D1-7	Run-in period	Visit #2 Randomisation visit D1 ⁽¹⁾	Visit #3 D8 (± 1) Optional visit⁽⁶⁾	Visit #4 D35 (± 3)	Visit #5 Final Visit D84 (± 7) Or Premature withdrawal
	First ophthalmologist investigator	Preservative free artificial tears Hydrabak®	First ophthalmologist investigator	First ophthalmologist investigator	First ophthalmologist investigator	First ophthalmologist investigator
Informed consent	X		X	X	X	X
Demography	X					
Ocular medical and surgical history	X					
Systemic medical and surgical history	X					
Previous and concomitant ocular/non ocular treatments	X					
History of Dry Eye	X					
DEQ-5	X					
OSDI score						
Ocular symptoms	X					
Ocular symptoms upon instillation ⁽²⁾						
Far best-corrected visual acuity	X					
Conjunctival hyperaemia (McMonnies photographic scale)	X					

Slit lamp examination	X		X		X		X	
TBUT	X		X		X		X	
Oxford 0-15 grading scheme (corneal staining by fluorescein, temporal and nasal staining by lissamine)	X		X		X		X	
Van Bijsterveld score green (lissamine staining)/optional examination ⁽⁷⁾	X		X		X		X	
Schirmer test (without anaesthesia)								
Verification of inclusion/exclusion criteria	X		X		X		X	
Tolerance assessment by the investigator					X		X	
Tolerance assessment by the patient					X		X	
Performance assessment by the investigator					X		X	
Urinary pregnancy test ⁽²⁾	X				X		X	
Adverse events			X	X	X	X	X	X
Dispensation of the run-in treatment	X							
Run-in treatment compliance								
Dispensation of the IMD ⁽³⁾			X			X		
IMD compliance ⁽³⁾						X		X
Evaluation of Optical Scattering Index (OSI) using double pass aberrometry ⁽⁴⁾					X		X	

Impression cytology (HLA-DR) Only for patients with severe Dry Eye ⁽⁵⁾			X						X	
---	--	--	---	--	--	--	--	--	---	--

- (1) No instillation of preservative free artificial tears (Hydrabak®) at least 6 hours before the randomisation visit.
- (2) Urinary pregnancy test to be done for childbearing potential women.
- (3) By the second investigator (or the designated site team member) responsible for dispensing, explications of dosing regimen,
- (4) The parameters will be measured only in investigator sites equipped with Optical Quality Analysing System (OQAS)
- (5) Severe Dry Eye will be defined based on the following criteria: OSDI \geq 33 and/or Corneal Fluorescein Staining \geq 3 at the baseline visit (Day 1).
- (6) This visit can be performed if the investigator and /or the patient thinks it is necessary.
- (7) This examination is not mandatory

ABBREVIATIONS

ADE	Adverse Device Effect
ADDE	Aqueous Deficient Dry Eye
AE	Adverse Event
ALCOA	Attributable, Legible, Contemporaneous, Original and Accurate
ANCOVA	Analysis of Covariance
ATC	Anatomical Therapeutic Chemical
ASADE	Anticipated Serious Adverse Device Effect
AUF	Arbitrary Units of Fluorescence
BCVA	Far Best-corrected visual acuity
CIP	Clinical Investigational Plan
CMH	Cochran-Mantel-Haenszel test
e-CRF	Electronic Case Report Form

2 IDENTIFICATION AND DESCRIPTION OF THE INVESTIGATIONAL MEDICAL DEVICE

2.1 Summary description of the investigational medical device (IMD) and its intended purpose

T2259 device is an isotonic neutral, clear and colourless solution developed to protect, hydrate and lubricate the eye. It contains Trehalose and Sodium Hyaluronate (SH).

T2259 device is packed in a multidose, white polyethylene ABAK® system bottle. The ABAK® container is a multidose eye-drop delivery system in which non-preserved solutions are entirely protected from microbial contamination by a membrane filter with very low porosity (0.2 µm). This ABAK® dispenser is already used for several currently marketed eye drops.

2.2 Manufacturing

T2259 device is manufactured by FARMILA-THEA Farmaceutici SpA, [name] in accordance with the European Union (EU) Good Manufacturing Practice (GMP), including the EU GMP Annex 13.

The IMD will be packaged by approved contractor in accordance with Good Manufacturing Practices (GMP).

The legal manufacturer of T2259 according to the directive 93/42 CEE is Laboratoires Théa.

The process uses techniques and equipment which the manufacturer is experienced with and which are fully controlled, since FARMILA-THEA already produces several ophthalmic preparations.

2.3 Intended purpose of the IMD in the proposed clinical investigation

T2259 eye drops are intended to protect, hydrate and lubricate in dry eye patients with superficial keratitis.

2.4 The populations and indications for which the IMD is intended

T2259 eye-drops are intended to be used in dry eye patients with superficial keratitis.

2.5 Description of the IMD

T2259 is an isotonic neutral, clear and colourless solution to protect, hydrate and lubricate the eye.

T2259 is packaged in a multidose white polyethylene ABAK® system bottle. The ABAK® container is a multidose eye-drop delivery system in which non-preserved solutions are entirely protected from microbial contamination by a membrane filter with very low porosity (0.2 µm). The dispenser is already used in several currently marketed eye drops.

The composition and function of the different ingredients of T2259 are detailed in [Table 3](#).

The excipients of the T2259 eye-drops (trometamol, sodium chloride, hydrochloric acid and water for injections) are well-known and commonly used in ophthalmic formulations.

Table 3 Investigational medical device T2259

Names of ingredients	Percentage formula (g/100 ml)	Function	Reference to standards
Water for injections	qsp 100 ml	Vehicle	Current Eur. Ph. [0169]
Trehalose*	6.00	Lubricating, hydrating agent	Current Eur. Ph. [2297]
Sodium Hyaluronate**	0.20	Lubricating, hydrating agent	Current Eur. Ph. [1472] and Certificate of Suitability
Sodium chloride	0.15	Isotonising agent	Current Eur. Ph. [0193]
Trometamol	0.242	pH buffer	Current Eur. Ph. [1053]
Hydrochloric acid, concentrated***	ad pH 7.0	pH adjustment	Current Eur. Ph. [0002]

* The quantity of Trehalose dihydrate is adjusted as a function of its titre and water content

** The quantity of Sodium Hyaluronate is adjusted as a function of its water content

*** Used under the form of a 1N solution for pH adjustment

[figure not shown]
2.6 Packaging and Labeling

The originality of the product resides in its packaging suitable for preservative-free multi-dose eye-drop presentations, thus avoiding the toxic and allergenic effects of the latter on the cornea.

T2259 is presented in a bottle (Figure 1), consisting in a polyethylene white opaque bottle which has an insert in its neck. The insert is made of two parts:

- The dropper device, to which is joined an antimicrobial membrane with a pore size of 0.2 μm , which protects the bottles contents from external contamination;
- The dropper device holder to which the dropper device is welded and which seals the bottle. The dropper device holder contains a porous material which controls the flow of eye drops onto the filter membrane and prevents the membrane from being in contact with the eye drops solution before first use.

Figure 1 ABAK® container

Each study site will receive one container (Final container).

Each of these containers contains two secondary containers:

- One container for treatment period Day 1 to Day 35 ;
- One container for treatment period Day 35 to Day 84.

[figure not shown]
Secondary containers for period Day 1 to Day 35 contain two bottles of the IMD. Secondary containers to be dispensed at Day 35 contain three bottles of the IMD.

Thus each patient receives up to five bottles of IMD during the study.

Bottles are labeled as shown below.

Figure 2 IMD: labeling of each primary bottle

For T2259:

Or

For Vismed® Multi:

[figure not shown]

Figure 3 Labeling of secondary containers for period Day 1 to Day 35 and Day 35 to Day 84

For T2259:


Laboratoires THEA- [name] [name] [contact]
 
 LT2259-001 Treatment Kit No.: KXXXX Batch No.: XX Expiry date: mm/YYYY Period Day 1 – Day 35 
 
Cardboard box containing 2 vials of 10 ml of T2259 Eye drops/Ocular use Dosage: One drop 2 to 4 times daily in the conjunctival cul-de-sac in each eye. Directions for use: Do not allow the tip to come into contact with the eye or eyelids. Put the cap back after use. Keep at temperature below 25°C Use within 2 months after opening. For clinical trial use only. Keep out of the reach of children. For topical ocular use only.
 
Prof/Dr _____ Tel: _____
	
Laboratoires THEA
 
 LT2259-001 
 
 Treatment: KXXXX PERIOD Day 1 – Day 35 
 
 Batch No.: XX Expiry date: mm/YYYY 

---	--

Laboratoires THEA- [name] [name] [contact]
 
 LT2259-001 Treatment Kit No.: KXXXX Batch No.: XX Expiry date: mm/YYYY Period Day 35 – Day 84 
 
Cardboard box containing 3 vials of 10 mL of T2259. Eye drops/Ocular use Dosage: One drop 2 to 4 times daily in the conjunctival cul-de-sac in each eye. Directions for use: Do not allow the tip to come into contact with the eye or eyelids. Put the cap back after use. Keep at temperature below 25°C Use within 2 months after opening. For clinical trial use only. Keep out of the reach of children. For topical ocular use only.
 
Prof/Dr _____ Tel: _____
	
Laboratoires THEA
 
 LT2259-001 
 
 Treatment: KXXXX PERIOD Day 35 – Day 84 
 
 Batch No.: XX Expiry date: mm/YYYY 

---	---

For Vismed® Multi:


Laboratoires THEA- [name] [name] [contact]
 
 LT2259-001 Treatment Kit No.: KXXXX Batch No.: XX Expiry date: mm/YYYY Period Day 1 – Day 35 
 
Cardboard box containing 2 vials of 15 mL of Vismed® Multi Eye drops/Ocular use Dosage: One drop 2 to 4 times daily in the conjunctival cul-de-sac in each eye. Directions for use: Do not allow the tip to come into contact with the eye or eyelids. Put the cap back after use. Keep at temperature below 25°C Use within 2 months after opening. For clinical trial use only. Keep out of the reach of children. For topical ocular use only.
 
Prof/Dr _____ Tel: _____
	
Laboratoires THEA
 
 LT2259-001 
 
 Treatment: KXXXX PERIOD Day 1 – Day 35 
 
 Batch No.: XX Expiry date: mm/YYYY 

---	--

Laboratoires THEA- [name] [name] [contact]
 
 LT2259-001 Treatment Kit No.: KXXXX Batch No.: XX Expiry date: mm/YYYY Period Day 35 – Day 84 
 
Cardboard box containing 3 vials of 15 mL of Vismed® Multi Eye drops/Ocular use Dosage: One drop 2 to 4 times daily in the conjunctival cul-de-sac in each eye. Directions for use: Do not allow the tip to come into contact with the eye or eyelids. Put the cap back after use. Keep at temperature below 25°C Use within 2 months after opening. For clinical trial use only. Keep out of the reach of children. For topical ocular use only.
 
Prof/Dr _____ Tel: _____
	
Laboratoires THEA
 
 LT2259-001 
 
 Treatment: KXXXX PERIOD Day 35 – Day 84 
 
 Batch No.: XX Expiry date: mm/YYYY 

--	---

Figure 4 Final packaging of IMD

Laboratoires THEA- [name] [name] [contact]	
LT2259-001 Treatment Kit No.: KXXXX	
Eye drops/Ocular use This cardboard carton contains: -2 cardboard boxes containing a total of 5 vials of T2259 -or 2 cardboard boxes containing a total of 5 vials of Vismed® Multi Batch No.: Expiry date: Dosage: One drop 2 to 4 times daily in the conjunctival cul-de-sac in each eye. Directions for use: Do not allow the tip to come into contact with the eye or eyelids. Put the cap back after use. Keep at temperature below 25°C Use within 2 months after opening. For clinical trial use only. Keep out of the reach of children. For topical ocular use only.	
Prof/Dr _____	Tel: _____

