6 DESIGN OF THE CLINICAL INVESTIGATION

6.1 General

The chosen methodology and criteria correspond to the standard usually used in the recent clinical trials in DES (HAS Optive, 2011).

Thus, this is a multicentre, randomized, investigator-masked, two parallel groups (T2259 versus Vismed® Multi) investigation in dry eye patients with superficial keratitis. The investigation will be performed in France, in Spain, in Slovakia and in Poland.

Multicenter (and multi-investigator) design will provide the possibility of recruiting the subjects from a wider population and of using the device in a broader range of clinical settings, thus presenting an experimental situation that is more typical of future use. In this case, the involvement of a number of investigators also gives the potential for a wider range of clinical judgment concerning the value of the therapeutic intervention. In addition, it is also a practical mean of accruing sufficient subjects to satisfy the study objective within a reasonable timeframe.

Because of a different visual aspect of the tested eye-drops, a double-masked comparison is not possible. Thus an investigator-masked method will be used. The identity of the IMD provided to each patient and the data concerning the instillation schedule will not be known by the investigator in charge of the examinations and of performance and safety assessments. The two different treatment units will be identical in external appearance in order to respect the randomisation. A second investigator (a physician) will dispense medications allowing to mask the first ophthalmologist investigator (who will be in charge of all examinations and assessments), and patients will be instructed not to disclose drug information with other staff members or the first investigator.

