6.2.2 Masking

This will be an investigator-masked clinical study. The **first ophthalmologist investigator** will remain masked to the IMD. He will NOT dispense or receive the returned IMD from the patients.

Masking will be achieved by providing the 2 IMD (T2259 and Vismed® multi) in identical cardboard and by identifying each IMD by a treatment number.

The **second ophthalmologist** investigator will be in charge of IMD dispensation, accountability and of patient questioning.

The code should not be broken except:

- In case of a medical emergency (where knowledge of the IMD received would affect the treatment of the emergency);
- Or when it is a regulatory requirement.

If an emergency code breaking becomes necessary, the investigator should notify the Sponsor, if possible, prior to breaking the code. The investigator and/or pharmacist are responsible for accessing the Interactive Web Response System to obtain the identity of the IMD allocated to the patient. When a code is broken, the date, time and reason must be recorded in the patient's source documentation as well as in the e-CRF, and in any associated AE report. The identity of the IMD should not be disclosed in these documents.

Further to a USADE assessment by the Global Drug Safety & Medical Information Department, the code might be broken for reporting purposes. The relevant Laboratoires Théa, CRO, and investigator staff remains unaware of the identification of the IMD.

The overall randomisation list will be broken only for data analysis after database lock.

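### Protocol 6.2.2 says identical cardboard and a treatment number achieve masking, but the period boxes given to patients name the product, and no step keeps returned packs from the grader before the Day 35 staining grade

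*Protocol*

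**What the plan says.** Protocol 6.1 explains that the two eye drops look different, so only the investigator is masked. It adds: "The two different treatment units will be identical in external appearance in order to respect the randomisation". Section 6.2.2 gives the means: "Masking will be achieved by providing the 2 IMD (T2259 and Vismed® multi) in identical cardboard and by identifying each IMD by a treatment number".

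Section 2.6 describes three packaging levels: bottles, two period boxes per patient (Day 1 to 35 and Day 35 to 84), and an outer carton. The printed text for the period boxes (Figure 3) differs by arm:

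- T2259, first period: "Cardboard box containing 2 vials of 10 ml of T2259"
- Comparator, first period: "Cardboard box containing 2 vials of 15 mL of Vismed® Multi"
- Comparator, second period: "Cardboard box containing 3 vials of 15 mL of Vismed® Multi" (the T2259 box for this period has three 10 mL vials)

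The outer carton (Figure 4) is neutral. It carries a kit number and lists both possibilities: "2 cardboard boxes containing a total of 5 vials of T2259", followed by "or 2 cardboard boxes containing a total of 5 vials of Vismed® Multi".

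Under 6.2.3 someone other than the grader opens the treatment unit. The patient gets one box on Day 1 and another on Day 35, and is asked to return unused product and used containers. Section 11 has products returned when asked for. Sections 6.4.4 and 6.4.5 set an order for the visit procedures, with the first investigator's examinations ahead of the second investigator's tasks.

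**The concern.** The primary endpoint is a 0 to 15 staining grade that the ophthalmologist assigns by matching the eye to reference panels. The same person rates performance and tolerance. Patients and the dispensing investigator are not masked, so the grader's ignorance of the allocation is the main protection against biased grading.

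The masking section describes packaging that does not match the label text for the boxes patients receive. If such a box or its bottles are visible when the patient sits down for the Day 35 examination, the grader can learn the allocation just before recording the primary outcome. In a non-inferiority trial, grading that leans towards T2259, or that treats a worse arm as similar, makes success easier. A lean the other way would make it harder.

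**Working it through.** **Step 1: which packaging level is identical?**

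| Level | What the label shows | Who handles it |
|---|---|---|
| Outer carton (2.6, Figure 4) | Kit number; both products as alternatives | Opened by the dispensing investigator (6.2.3) |
| Period box (2.6, Figure 3) | Product name or code; 10 mL or 15 mL vials; kit number. A second panel shows the kit number without the product | Given to the patient on Day 1 and Day 35 (6.2.3) |
| Bottle (2.6, Figure 2) | Label not shown in the text available | Used by the patient |

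The wording in 6.2.2 fits the outer carton. It does not fit the period box, which is the level that leaves the site with the patient.

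**Step 2: can an identifying pack reach the grader before the Day 35 grade?**

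- Return of product and used containers is required (6.2.3). No visit is fixed, and section 11 says only that return is on request.
- The second investigator checks compliance at Day 35 and Day 84 (6.8.4), and section 11 assesses compliance from the accountability log together with questions to the patient. Return at Visits 4 and 5 is therefore the natural reading, though not an explicit instruction.
- Both visit lists place the grader first. Followed as written, a patient who brings packs back meets the grader before the person who collects them.
- Section 6.2.2 bars the grader from receiving returned product. It does not bar the grader from seeing it, and neither visit list has a hand-over step.

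So exposure is possible under the plan as written, but the plan does not make it certain or say how often it would occur.

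**Step 3: which visits count?** The primary grade is taken at Visit 4. A pack seen at Visit 5 can affect only the Day 84 secondary endpoints and ratings, with one exception: a premature withdrawal visit follows the Visit 5 list, and SAP 4.3 may reassign it to Day 35.

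**Step 4: scale.** No figure in the plan depends on masking, so there is none to reproduce for this point. As a check on the inputs from protocol 7.5 (38 per arm, SD 2.5, margin 2, one-sided 2.5%), 38 per arm gives 93.1% power by the t-test, consistent with the stated minimum of 90%.

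- SE of the difference = 2.5 × √(2/38) = 0.574
- 95% half-width = 1.993 × 0.574 = 1.14
- Largest observed difference that still passes = 2 − 1.14 = 0.86 point

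The 0.86 follows from sample size, SD and margin alone. It does not measure this defect. To see what a grading shift could do, suppose the true difference equals the margin of 2 and the mean difference is moved towards T2259 by b. The chance of wrongly concluding non-inferiority is P(T > 1.993), where T is noncentral t with 74 degrees of freedom and noncentrality b/0.574:

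| Assumed shift b in the mean difference | False non-inferiority |
|---|---|
| 0 | 2.5% |
| 0.075 | 3.4% |
| 0.25 | 6.3% |
| 0.5 | 13.6% |
| 1.0 | 40.6% |

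The shift b averages over masked and unmasked patients. For example, a 0.3-point shift in 25% of one arm gives b = 0.3 × 0.25 = 0.075. All values of b are assumptions; the documents supply none.

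**The case against.** The strongest reply is that masking does not rest on the boxes alone. The grader does not dispense or take back product, a second investigator handles dispensing, accountability and questioning, and patients are instructed not to reveal their treatment. The treatment unit in 6.1 is most naturally the outer carton, whose label is neutral, so 6.1 need not conflict with Figure 3 at all. This stands, and it narrows the contradiction to 6.2.2 against the period-box labels.

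A reader might go further and infer that every randomised patient carries a named box into both post-baseline visits. The documents do not support that. They fix no visit for the return, and section 11 speaks of collecting bottles, without saying that the cardboard comes back or enters the examination room. A reader might also take the 0.86-point passing zone as showing that small grading shifts in unmasked cases are decisive. It does not show that, because the effect also depends on the share of patients unmasked, which is unknown.

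It is also fair that relabelling alone would do little. Bottles of 10 mL and 15 mL stay distinguishable, and the SAP (5.1) already reports 101 randomised patients.

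None of this closes the remaining gap: no text keeps a returned pack out of the grader's view before the Day 35 grade.

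**Conclusion.** The point holds in a limited form. Section 6.2.2 does not describe the period boxes that patients receive, and the visit order allows an identifying pack to be present when the primary endpoint is graded. The existing safeguards reduce this risk but do not address sight of returned packs.

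The size and direction of any bias are unknown. The illustration runs from negligible to material according to an assumed shift, and rests on the planned 38 per arm, SD 2.5 and a true difference at the margin. It is not evidence that grading was biased or that masking failed. The change is worth making because the gap touches a subjective primary outcome and is cheap to close.

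**What to change.** 1. In protocol 6.4.4 and 6.4.5, have the second investigator collect returned product and packaging before the first investigator's examination and keep them out of the grader's sight. This is the main protection, since neutral boxes would not hide the different bottles.
2. Reconcile 2.6, 6.1 and 6.2.2 by stating which packaging level is identical. For any kits still to be labelled, put the outer carton's either/or wording on the inner boxes, without the volume, plus kit number and period.
3. Where visits are already done, record suspected unmasking of the grader and review it at the blind review meeting. The deviation categories in SAP 6.2 have no masking entry, so it would otherwise fall under the residual category.

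The cost is a small change in visit flow, one sentence in each of two visit lists, and a modest relabelling cost if kits remain to be produced. The second investigator is already present at both visits, so no staff are added.
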